6.3.1 Participant numbering

Each participant is identified in the study by a participant Number (participant No.) that is assigned when the participant is first enrolled for screening and is retained as the primary identifier for the participant, unless the participant is re-screened. The participant No. consists of the Center Number (Center No.) (as assigned by Novartis to the investigative site) with a sequential participant number suffixed to it, so that each participant is numbered uniquely across the entire database. Upon signing the informed consent form, the site will use the electronic data capture system to assign the participant the next sequential participant No.

The investigator or designated staff will contact the Interactive Response Technology (IRT) and provide the requested identifying information to register the participant. Once assigned, the participant No. must not be reused for any other participant and the participant No. for that individual must not be changed, unless the participant is re-screened. If the participant fails to start treatment for any reason, the reason will be entered into the appropriate eCRF page and IRT should be notified as soon as possible. Re-screening is allowed once for participants that were initially screen failures for any reason. All eligibility criteria must be re-checked and met prior to enrollment of the participant into the study. A new participant No. should be assigned for all re-screened participants.

6.3.2 Treatment assignment, randomization

This study is open label and non-randomized.

Prior to dosing at Cycle 1 Day 1, participants who fulfill all the inclusion/exclusion criteria will be enrolled via IRT and a treatment number will be provided for the study treatments sabatolimab, venetoclax, and azacitidine.

The Investigator (or delegate) will call or log on to the IRT and confirm that the participant fulfills all the inclusion/exclusion criteria by completing the eligibility criteria checklist embedded in the system. The IRT will assign a unique medication number for the first package of study treatments to be dispensed to the participant.

6.4 Treatment blinding

The study is open-label with no blinding.

6.5 Dose escalation and dose modification

Two dose levels of sabatolimab, 400 mg Q4W (Safety run-in (Part 1) cohort 1) and 800 mg Q4W (Safety run-in (Part 1) cohort 2) will be evaluated. Intra-participant dose escalation is not permitted. Guidance for dose modifications is provided in Section 6.5.1.

6.5.1 Dose escalation guidelines

6.5.1.1 Sabatolimab dose level and regimen

Sabatolimab will be given at 400 mg every 4 weeks in the first approximately 6 enrolled participants (at least 3 evaluable participants) (cohort 1 of the Safety run-in (Part 1)). If this dose level is considered safe, sabatolimab will be given at 800 mg every 4 weeks in the next approximately 12 participants (at least 9 evaluable participants) (cohort 2 of the Safety run-in (Part 1)).

In case the combination does not meet overdose criteria at the cohort 1 of Safety the run-in (Part 1) (participants treated with sabatolimab at 400 mg Q4W); but meets the overdose criteria at cohort 2 of the Safety run-in (Part 1) (participants treated with sabatolimab at 800 mg Q4W), the Expansion (Part 2) will not be opened. The Expansion (Part 2) will be opened only if the two cohorts does not meet the overdose criteria consecutively.

6.5.1.2 Provisional dose levels

Table 6-3 below describes the starting dose and the dose levels that may be evaluated during the Safety run-in (Part 1) of this trial.

Dose level	Proposed dose* (Q4W)	Increment from previous dose
1	400 mg	(starting dose)
2	800 mg	100%

 Table 6-3
 Provisional dose levels of sabatolimab during Safety run-in (Part 1)

* In combination with azacitidine (75 mg/m² Day 1-7) + venetoclax (400 mg Day 1-14)

6.5.1.3 Guidelines for assessing tolerability

For the purpose of assessing the risk of overdosing (as defined by EWOC criterion, see details below) of sabatolimab in combination with azacitidine and venetoclax, at each sabatolimab dose level, after the required number of evaluable participants, at least 3 participants for cohort 1

(Part 1) and at least 9 participants for cohort 2 (Part 1), have been included, and observed for at least 2 cycles, a safety review meeting will be conducted.

Participant will be considered evaluable for DLT if:

 \cdot Participant has received 2 infusions of sabatolimab at the assigned dose level in Q4W dosing regimen, and has taken at least 75 % of the planned dose of azacitidine and venetoclax (i.e. for 2 cycles: 11 doses of azacitidine out of the 14 doses planned and 21 doses of venetoclax out of the 28 doses planned), and participant has had safety assessments for a minimum period of 2 cycles (from Cycle 1 Day 1 to the end of Cycle 2). Participants receiving a reduced dose of venetoclax due to co-administration of strong or moderate CYP3A4 inhibitors or P-gp inhibitors as described in Table 6-2, will be considered to have received the planned dose.

or

 \cdot Participant has experienced a DLT within the DLT observation period from first dose of sabatolimab to the end of Cycle 2. Note that participants who experience toxicity that meets the criteria for DLT but occurs prior to the first dose of sabatolimab will be considered not evaluable.

At the Safety Review Meetings, Investigators and Novartis study personnel will review all relevant data available from the ongoing study including safety information, DLTs, time of occurrence of DLT, supported by all CTCAE v5.0 \geq Grade 2 toxicity data during the first 2 cycles of the study treatment, and pharmacokinetic data from evaluable participants.

The decision will be guided by a Bayesian model with EWOC principle evaluating the probability of DLT. For each cohort of the Safety run-in, the probability of excessive toxicity (i.e. DLT rate \geq 33%) will be assessed after the required number of evaluable participants have been treated and observed for up to end of Cycle 2. If the EWOC criteria is satisfied (probability of excessive toxicity is lower than 25%), the Bayesian model will recommend to start enrollment to either cohort 2 (Part 1) or the Expansion Part (Part 2).

At the safety review meetings, the available toxicity information (including adverse events and laboratory abnormalities that are not DLTs), the time (days from start of therapy) of occurrence of DLT, the recommendations from the Bayesian analysis, and the available PK and pharmacodynamic information will all be evaluated by the Investigators and Novartis study personnel. Once the results of the safety review meeting are available, the investigator will receive written confirmation from Novartis indicating that the results of the Safety run-in part (Part 1) were evaluated and that it is permissible to start enrollment to either cohort 2 (Part 1) or the Expansion Part (Part 2).

6.5.2 Definitions of dose limiting toxicities (DLTs)

Dose-limiting toxicities will be collected and evaluated in participants enrolled to the Safety run-in part. A dose-limiting toxicity (DLT) is defined as an adverse event or abnormal laboratory value considered by the Investigator to be at least possibly related to sabatolimab as a single contributor or in combination with other component(s) of study treatment that occurs during the DLT observation period and meets any of the criteria included in Table 6-4. The DLT observation period is Cycle 1 Day 8 (starting from the first infusion of sabatolimab) to the

Novartis	Confidential	Page 52 of 143
Amended Protocol Version 02 (Clean)		Protocol No. CMBG453B12203

end of Cycle 2. The National Cancer Institute Common Terminology Criteria for Adverse events (NCI CTCAE) version 5.0 will be used for all grading.

If a participant experiences a DLT (during the DLT observation period) then study treatment must be interrupted and may be permanently discontinued depending on the severity of the DLT, if the DLT resolves to CTCAE Grade 1 or baseline value, the participant may continue to receive study treatment following consultation with the Novartis medical monitor.

The investigator must notify the sponsor immediately of any unexpected CTCAE grade ≥ 3 adverse events or laboratory abnormalities.

Toxicity	DLT Criteria
Hematology	Because marrow suppression is an expected consequence of MDS and its therapy, for participants participating in this study, only persistent grade 4 neutropenia, thrombocytopenia and pancytopenia beyond Day 42 from the start of a study treatment cycle and is not related to the underlying disease will be considered to be a DLT (bone marrow evaluation may be required to determine if the bone marrow suppression is due to the underlying disease). OR Febrile neutropenia CTCAE Grade 4 OR Sepsis CTCAE Grade 4
Vascular disorders	Hypertension CTCAE Grade 3 persisting for > 7 days after treatment is administered, despite adequate antihypertensive therapy
General disorders and administration site conditions	Infusion reaction CTCAE Grade 3 that does not resolve to Grade 1 within 72 hours or CTCAE Grade 4 of any duration
Immune	Immune-related adverse events \geq CTCAE Grade 3 persisting > 7 days after starting appropriate treatment* (e.g. with corticosteroids)
Occular	Eve pain or vision decreased:

Table 6-4Criteria for defining dose-limiting toxicities during the Safety run-in
(Part 1)

Toxicity	DLT Criteria
	\geq CTCAE Grade 2 that does not improve to Grade 1 severity within 2 weeks after the initiation of topical therapy
	OR
	Eye pain or vision decreased that requires systemic treatment
Pulmonary	Pneumonitis of non infectious etiology ≥ CTCAE Grade 2 persisting > 7 days despite treatment with corticosteroids
	Pneumonitis of non infectious etiology \geq CTCAE Grade 3
Skin and subcutaneous tissue disorders	Photosensitivity \geq CTCAE Grade 3 for $>$ 7 days after treatment
	Rash \geq CTCAE Grade 3 for $>$ 7 days after treatment
	Rash CTCAE Grade 4
	Any severe skin reactions (such as Toxic Epidermal Necrolysis, Steven Jones Syndrome)
Gastrointestinal disorders	Diarrhea CTCAE Grade $\geq 3 \geq 48$ hrs., despite the use of anti-diarrhea therapy
	Nausea/ vomiting CTCAE Grade $\ge 3 \ge 48$ hrs., despite the use of anti-emetic therapy
	Pancreatitis CTCAE Grade ≥ 3
Investigations	Blood bilirubin increase \geq CTCAE Grade 2 (caused by increased direct bilirubin) with ALT and/or AST \geq CTCAE Grade 2, without evidence of cholestasis and with absence of any alternative cause likely explaining the combination of increased ALT or AST and blood bilirubin
Other	Other clinically significant toxicities, including a single event or multiple occurrences of the same event that lead to a dosing delay of > 7 days in cycle 1, or result

Toxicity	DLT Criteria
	in an inability to deliver $\geq 75\%$ of the planned dose intensity for any of the study drugs in a cycle of treatment because of treatment-related toxicity.
	Any other unacceptable toxicity encountered by a participant as determined by the Investigators and Novartis.
	Any grade 4 non-hematologic toxicity that is not clearly related to a cause other than the study treatment under study.
Exceptions to DLT Criteria	

· Grade 3 fatigue, asthenia, fever, anorexia, or constipation

 \cdot Grade 3 nausea, vomiting or diarrhea not requiring tube feeding, total parenteral nutrition, or prolonged hospitalization

 \cdot Infection, bleeding, or other expected direct complication of cytopenias due to active underlying disease

 \cdot Grade 3 or 4 tumor lysis syndrome if it is successfully managed clinically and resolves within 7 days without end-organ damage

· Grade 3 or 4 isolated laboratory abnorr	malities that last ≤ 3 days
---	----------------------------------

*Unless	otherwise	specified	for	orga	n-specific	immu	ne-related	DLTs
\cdot CTCAE	version	5.0	will	be	used	for	all	grading

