reported also promising efficacy and acceptable safety profile of the doublet of venetoclax and azacitidine in participants with higher-risk MDS. Despite the improved efficacy suggested by the addition of venetoclax to azacitidine in higher-risk MDS, a significant unmet medical need remains as a substantial number of participants still do not achieve durable CR (complete response).

2 Objectives and endpoints

The objectives and associated endpoints are presented in Table 2-1 below:

Objective(s)			ndpoint(s)
Primary objective(s)			ndpoint(s) for primary objective(s)
•	Safety run-in (Cohort 1 and Cohort 2 of Part 1)	•	Incidence of DLTs between Cycle 1 Day 8 and end of Cycle 2
	To determine whether sabatolimab is safe when added to azacitidine + venetoclax in participants with high or very high risk MDS per IPSS-R criteria		
•	Cohort 2 of Safety run-in (Part 1) and Expansion (Part 2)	•	Proportion of participants from cohort 2 of Part 1 and Part 2 achieving CR according to investigator
	To determine the complete remission (CR) rate of sabatolimab in combination with azacitidine and venetoclax in participants with high or very high risk MDS as per IPSS- R criteria treated with sabatolimab at 800 mg Q4W.	assessment (per modified IWG-MDS - Che criteria). CR is defined as follow: bone mar <=5%, hemoglobin level \geq 10 g/dL, platele 100*10^9/L, neutrophils count \geq 1.0*10^9/L of blasts in peripheral blood (Please see Se for estimand definition).	assessment (per modified IWG-MDS - Cheson 2006 criteria). CR is defined as follow: bone marrow blasts <=5%, hemoglobin level \geq 10 g/dL, platelets count \geq 100*10^9/L, neutrophils count \geq 1.0*10^9/L, absence of blasts in peripheral blood (Please see Section 12.4 for estimand definition).
Se	condary objective(s)	En	idpoint(s) for secondary objective(s)
•	Safety run-in (Part 1) and Expansion (Part 2)		
•	To assess the [CR + marrow complete remission (mCR)] rate	•	Proportion of participants with [CR + marrow complete remission (mCR)] according to investigator assessment by dose level for the safety run-in part (cohort 1 (400 mg Q4W) and cohort 2 (800 mg Q4W)) and for participants treated with sabatolimab 800 mg (Q4W) (cohort 2 of safety run-in and expansion parts).

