12.1 Analysis sets

The Full Analysis Set (FAS) comprises all participants who received at least one dose of study treatment.

The Safety Set includes all participants who received at least one dose of study treatment.

The Dose Determining Set (DDS) includes all participants from the FAS enrolled the Safety run-in part who met the minimum exposure criterion and had sufficient safety evaluations, or experienced a dose limiting toxicity (DLT) during the first 8 weeks of dosing (two cycles).

A participant has met the minimum exposure criterion if the participant has received during the first 2 cycles 2 infusions of sabatolimab at the assigned dose level in Q4W dosing regimen, and has taken at least 75 % of the planned dose of azacitidine and venetoclax (i.e. for 2 cycles: 11

doses of azacitidine out of the 14 doses planned and 21 doses of venetoclax out of the 28 doses planned).

Participants who do not experience a DLT during Cycles 1 and 2 are considered to have sufficient safety evaluations if they have been observed for at least 56 days following the first dose, and are considered by both the sponsor and investigators to have enough safety data to conclude that a DLT did not occur.

The sabatolimab and venetoclax pharmacokinetic analysis sets include all participants from the Safety Set who provide at least one evaluable sabatolimab/venetoclax PK concentration.

For a concentration to be evaluable:

- Dosing information must be properly documented (data and time of administration).
- For pre-dose samples: the sample is collected before the next dose administration.

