12.4.1 Definition of primary endpoints and estimands

12.4.1.1 Safety run-in (Part 1)

For the Safety run-in part, the primary endpoint is the incidence of DLTs in the first 2 cycles of treatment for participants in the DDS.

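### Does a grade 4 cytopenia criterion that matures 15 days after the DLT window closes leave the reported DLT incidence undefined?

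*Protocol*

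**What the plan says.** Protocol Table 2-1 defines the Part 1 primary endpoint as "Incidence of DLTs between Cycle 1 Day 8 and end of Cycle 2", and section 12.4.1.1 repeats that "the primary endpoint is the incidence of DLTs in the first 2 cycles of treatment for participants in the DDS". Section 6.5.2 defines a DLT as an adverse event or abnormal laboratory value, at least possibly related to sabatolimab, "that occurs during the DLT observation period and meets any of the criteria included in Table 6-4". The hematology row of that table admits "only persistent grade 4 neutropenia, thrombocytopenia and pancytopenia beyond Day 42 from the start of a study treatment cycle", not explained by the disease. Grade 4 febrile neutropenia and grade 4 sepsis count without any duration. A later row adds "Any other unacceptable toxicity encountered by a participant as determined by the Investigators and Novartis".

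A participant without a DLT is evaluable under section 6.5.1.3 when, besides meeting the exposure rule, the "participant has had safety assessments for a minimum period of 2 cycles (from Cycle 1 Day 1 to the end of Cycle 2"). Section 12.1 requires that "they have been observed for at least 56 days following the first dose" and, as a second condition, that both the sponsor and the investigators judge them "to have enough safety data to conclude that a DLT did not occur". SAP 2.2.3 keeps that second condition and replaces the day count with two cycles. SAP 2.5.1.1 summarizes and lists DLTs falling in the evaluation period. SAP 2.1 sets each safety-review cut-off after two completed cycles, but takes everything up to database lock for the abbreviated report.

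**The concern.** The hematology row speaks of a treatment cycle in general, not of Cycle 1 alone. Yet on the planned schedule a cytopenia counted from Cycle 2 cannot complete its Day 42 requirement before the window shuts. If both onset and completion had to fall inside, the criterion could never operate for Cycle 2. If onset is enough, a participant could satisfy the minimum observation period and be counted as free of DLT before anyone could tell.

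Myelosuppression is the main reported toxicity of venetoclax with azacitidine (protocol section 1.1), so the situation is plausible. The statistic affected is the Part 1 primary endpoint. While the safety reviews lay ahead, it also fed the Bayesian overdose rule with its 25% limit.

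**Working it through.** **Inputs.** Cycle length 28 days (protocol section 8). Window from Cycle 1 Day 8 to the end of Cycle 2 (Table 2-1 and 6.5.2). Minimum observation 56 days (12.1). Threshold: beyond Day 42 of a cycle (Table 6-4). Hematology on Days 1, 8 and 22 of Cycles 1 and 2, then on Days 1 and 8 of each cycle (8.3.1).

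**The plan's own figure.** Two cycles = 2 × 28 = 56 days = 8 weeks, which agrees with section 12.1.

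**Day count, taking Day 1 as the cycle start.**
- Cycle 2 Day 1 = 28 + 1 = study Day 29.
- Cycle 2 Day 42 = 29 + 41 = Day 70, so the first day beyond it is Day 71.
- Gap = 71 − 56 = 15 days. If Cycle 2 starts s days late, the gap to the end of Cycle 2 is (71 + s) − (56 + s) = 15, unchanged.
- Counted from Cycle 1, the criterion is met on Day 43, which is 56 − 43 = 13 days before the window closes. It can be seen at Cycle 2 Day 22 (29 + 21 = Day 50).
- If Cycle 2 is taken to run until Cycle 3 actually starts, a Cycle 3 delay of d days moves the end to 56 + d. The gap closes at d = 15.

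**Which reading does the text support?** Section 6.5.2 sets two conditions: the event occurs in the window, and it meets a criterion. Only the first is dated. Other rows of Table 6-4 are built in the same way: grade 3 hypertension and immune-related events lasting more than 7 days, a grade 3 infusion reaction not settling in 72 hours, eye symptoms not improving in 2 weeks. Hypertension first treated on Day 52 could not exceed 7 days until after 52 + 7 = Day 59, which is also past Day 56. A completion rule would therefore cut late-onset events from several rows, and it would make the cycle-general wording of the hematology row empty for Cycle 2. Onset in the window, with the criterion allowed to mature later, gives every row a meaning.

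**Will the data be there?** Scheduled counts after the window fall on Day 57 (Cycle 3 Day 1), Day 64 (Cycle 3 Day 8) and Day 85 (Cycle 4 Day 1). Section 10.1.1 requires adverse events to be followed to resolution or permanence, with a new dated entry when a grade 3 or 4 event improves. Section 6.5.4 requires at least weekly follow-up for 4 weeks where treatment is interrupted or stopped for an adverse event or a clinically significant laboratory value. SAP 2.6.2.4 lists all grade 3 and 4 laboratory toxicities, SAP 2.6.2.1 lists all adverse events, and SAP 2.5.1.1 lists the DLTs.

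**Size of one case.** The shift is 1/n: 1/12 = 8.3 and 1/9 = 11.1 points in cohort 2; 1/6 = 16.7 and 1/3 = 33.3 points in cohort 1. With no other DLT in cohort 2, the exact 95% intervals are:

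| Scoring of one open case | DLTs / evaluable | Incidence | Exact 95% CI |
|---|---|---|---|
| Not a DLT | 0/12 | 0% | 0 to 26.5% |
| DLT | 1/12 | 8.3% | 0.2 to 38.5% |
| Left out of the set | 0/11 | 0% | 0 to 28.5% |
| Not a DLT | 0/9 | 0% | 0 to 33.6% |
| DLT | 1/9 | 11.1% | 0.3 to 48.2% |

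The intervals overlap heavily. The documents give no rate for cytopenia of this duration, so the expected number of cases cannot be derived.

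**The case for a change.** The strongest opposing case is that nothing says in so many words that onset governs. Section 6.5.1.3 speaks of a DLT experienced within the period and SAP 2.5.1.1 of DLTs occurring in it. Either can be read as asking for completion inside the window. The judgement clause in 12.1 decides who belongs to the Dose-Determining Set; it can hold a case back or exclude it, but it does not make it a DLT. The catch-all row is discretionary, and the word only in the hematology row leaves it unclear whether that row may be used for a cytopenia. At a safety review one case could have mattered. In Table 16-6, moving from 0/3 to 1/3 at 400 mg raises the probability of excessive toxicity from 0.058 to 0.262. After 1/4 in cohort 1, moving from 2/9 to 3/9 at 800 mg raises it from 0.154 to 0.331. Both steps cross 25%.

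Part of this stands. The wording is not explicit, and an open case could have been unresolved at a review cut-off. A count that is grade 4 on Day 64 and recovered on Day 85, with nothing in between, would remain undetermined because 85 − 64 = 21 days separate the scheduled samples.

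The rest does not carry. The clause in 12.1 need not score the case, since 6.5.2 and Table 6-4 do that once Day 42 of the cycle has passed. It has only to stop a premature classification as free of DLT, and nobody can properly conclude that no DLT occurred while a qualifying cytopenia is open. The phrases in 6.5.1.3 and SAP 2.5.1.1 are compatible with an event dated by its onset. The review decisions have been taken: SAP section 1 records the second meeting on 26-Sep-2022, the recruitment halt for reasons other than safety, and that Part 2 will not open.

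**Conclusion.** The 15-day gap is confirmed, but it is a gap in wording that analysts following the plan will fill correctly. An event with onset in the window counts once it meets the criterion, and the abbreviated report can apply this with data to database lock. Adding undetermined cases as DLTs in a sensitivity count would depart from the investigator-assessed definition in 6.5.2. It would be a preference, not a repair. A separate listing would largely duplicate those already planned.

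The conclusion rests on three assumptions: that 6.5.2 is read as written, with the timing attached to the event; that the sponsor and investigators apply the judgement clause to open cytopenias; and that follow-up of grade 4 events is recorded as section 10.1.1 requires. If they hold, no participant is misassigned for want of a rule, apart from a possible undetermined case between Days 64 and 85. If one were misassigned, a descriptive incidence would move by 8.3 to 11.1 points in cohort 2 or 16.7 to 33.3 points in cohort 1, with no decision attached to it.
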